Protocol: Development of Walk Assist Device to Improve Community Ambulation

PI – [name] [name] Department of Physical Medicine & Rehabilitation Northwestern University Rehabilitation Institute of Chicago [name] Ph: [contact] [contact] [contact]

Version Date: 4/16/10

I. Overview

We will assess a walk assist device (WAD) which assists flexion and extension at the hip joint to assist community walking/ambulation. Prototype model of this device has been developed by Honda Motor Corporation ®, Japan. This device: 1) will be simple to use in the clinical setting; 2) will be easily adjustable to alter the requirement of each subject; and, 3) will be able to quantify the amount of assistance required to facilitate normal community walking patterns. With the use of this device we will evaluate adaptations in walking performance following both over ground and body weight supported treadmill walking (BWSTT) in individuals with stroke. This information will help us identify the impact of an automated walking assistance device on lower extremity muscle activity, motor performance (kinematics), and corticospinal excitability after chronic neurological injury.

The assessment of WAD will be undertaken to determine the optimal use of the device tested on the treadmill and over ground in individuals with chronic motor unilateral stroke.

Testing procedures and informed consent procedures are described below.

II. Subject Population

Subject sample size of 12 stroke subjects will be sufficient to detect a significant difference, however considering attrition 15 subjects will be recruited. For the objective measures, power analysis yielded a sample size of 12 will be sufficient to detect a significant difference, however considering attrition 15 subjects will be recruited.

Subjects will be chosen to participate in this study, drawn from the Rehabilitation Institute of Chicago Research Registry.

Specific inclusion for participation of subjects includes:

- a. Stroke subjects with a history of unilateral, supratentorial, ischemic or hemorrhage stroke will be recruited, with lesion location confirmed by radiographic findings.
- b. All subjects who score > 10 on the Lower Extremity Motor Score (LEMS) developed previously to measure strength in SCI. For the LEMS criteria, preliminary data indicate that subjects with LEMS < 10 in the chronic stages do not recover walking.

- c. All subjects will be required to walk > 10 m over ground without physical assistance at self-selected walking speeds ≤ 0.8 m/s using assistive devices and bracing below the knee as needed. A criterion of 0.8 m/s is utilized to target participants with limited or minimal ambulation in the community. Subjects will be further stratified into those who walk < 0.4 m/s and > 0.4 m/s, identified as household vs. limited community ambulators, respectively.
- Range of motion (ankle: -10 to 30 deg, knee: 0 to 90 deg, hip: -10 to 40 deg) consistent with gait;
- e. Medically stable with medical clearance to participate (absence of concurrent illness, including unhealed decubiti, infection, cardiopulmonary disease, osteoporosis, active heterotrophic ossification or peripheral nerve damage in the lower limbs, history of traumatic head injury);
- f. Able to tolerate 30 minutes of upright (standing) position without orthostasis (decrease in blood pressure by 20 mmHg systolic and 10 mmHg diastolic; minimized with ambulatory population);
- g. Must not be undergoing concurrent physical therapy to eliminate effects of additional interventions;

 Patients prescribed medications for spasticity will not be excluded from participation but will be asked to maintain current levels of medication or inform the researcher if changes are necessary.

Specific exclusion for participation of subjects includes:

- a. Women of childbearing potential will not be excluded, although women who are pregnant will be excluded due to potential forces at trunk from BWS or pelvic assistance;
- b. Significant cardiorespiratory or metabolic disease that may limit exercise participation.
- c. Weights limit > 250 lbs (limit of most counter-weight safety systems).
- d. History of previous orthopedic or neurological conditions which may impair walking.
- e. Exclusion for TMS: pacemaker, metal implants in the head region, history of epilepsy or seizures, skull fractures or skull deficits, concussion within the last 6 months, unexplained recurring headaches, medications that lower seizure threshold, and pregnancy.
- f. Subjects with scores < 23 on the Mini Mental Status Exam will be excluded.

III. Evaluation of motor and walking performance using walk assist device

A. Clinical Assessment of motor and walking performance

For evaluation purposes and measures of walking progression, reliable and valid measures will be utilized to assess: a) lower extremity voluntary control; b); degree of walking independence; and, c) walking speed, endurance and temporal-spatial parameters.

- Assessment of strength, spastic motor behaviors and functional ambulation will be performed by a licensed physical therapist at the initial evaluation and during walking protocols.
 Assessment includes:
- Lower Extremity Motor Scores: to determine strength in the lower extremities

- Functional Independence Measure (FIM): extent of disability and societal limitations linked with functional limitations of ambulation.
- 10m walk: gait speed
- 6min walk: gait speed and distance
- GaitMat II (Equitest, Chalfont, PA): to detect temporal-spatial gait patterns.

B. Objective measure of motor and walking performance

Evaluation of the changes in walking performance with the use of the proposed WAD will be assessed using computerized gait analysis during independent stepping on an instrumented treadmill and during over ground walking. Specific outcome measures include: a) extent of lower extremity loading and ground reaction forces during independent treadmill stepping; c) peak treadmill speed at minimal body weight support; c) lower extremity kinematics during stepping, including peak hip, knee, and ankle joint kinematics during walking, and temporal-spatial gait parameters, and, d) timing of lower extremity EMG activity during treadmill stepping. In addition, metabolic costs will be determined. Metabolic costs will be collected using a portable metabolic system (K4b2, CosMed USA, Inc., Chicago). Metabolic measures will be obtained in sitting for 5 minutes prior to walking. Metabolic measures will be taken during un-assisted walking and device assisted walking for comparison. Subjects will return to their metabolic baseline between the walking trials. Metabolic measures will always be measured at sub-maximal levels and will be stopped 75% of target heart rates. Written approval from subject's physician will be obtained before allowing subjects to participate in sub-maximal graded treadmill test. Non-approval from physician will exclude the subject's participation only in the sub-maximal graded treadmill test; however they will be allowed to participate in the other tests involved in the study. Gait analysis

will be performed with use of a motion analysis system (Motion Analysis Corp. Santa Rosa, CA), which includes eight strategically positioned charge-coupled device video cameras (VC491; Oxford Metrics), a minicomputer (PDP 11/73; Digital Equipment, Maynard, Massachusetts), and software for the collection and analysis of the data. Twenty-one, 1-inch diameter spherical reflective markers will be placed over pre-determined anatomical landmarks on the trunk and extremities. The patient will walk on a treadmill with embedded bilateral force plates, and the position coordinates for the markers on both sides of the body will be recorded simultaneously at 120 Hz using phase-locked cameras. The recording technique and the software allow for the threedimensional reconstruction of the motion of all of the major joints of the upper and lower extremities. All of the patients will wear comfortable shoes, and each will walk at pre-determined (0.5 km/hr increments) and maximal speed. A harness attached to the suspension system will be used for all patients to prevent the patient from falling. Data will be collected at least three times for 30 sec at various speeds. In cases of visual occlusion of reflective markers during walking with assistance and/or devices, gait kinematics at the knee and hip will be detected by electrogoniometers placed bilaterally (Biometrics, Ltd, UK). The electrical activity of the TA, SOL, MG, VL, RF, and MH will be recorded bilaterally with a 32-channel dynamic EMG telemetry system (Noraxon Inc., Scottsdale, AZ), with surface electrodes sampling at 960 Hz. Force-plates (OR6; AMTI, Newton, Massachusetts) that are embedded in the treadmill will sample the ground-reaction forces at 960 Hz.

C. Objective measure of corticospinal excitability during walking:

Transcranial magnetic stimulation (TMS) will be performed while walking with and without the WAD. TMS is a safe, non-invasive, painless method of brain stimulation that has been widely used to study the physiology of the representations of muscles in the motor cortex in healthy and neurologically disordered individuals. Very short duration (< 1 ms) magnetic pulses are applied via an insulated wire coil placed on the intact scalp overlaying the motor cortical. Each pulse induces a motor evoked potential (MEP) in a target muscle that can be readily monitored by recording EMG from the muscle. Magnetic stimuli will be delivered from a Magstim 200 unit via a Magstim double cone coil (Magstim Company, Boston MA). Self adhesive disposable electrodes (Suretrace) with an inter-electrode distance of 2 cm will be applied over the muscle bellies of the quadriceps, hamstrings, ankle dorsiflexors and ankle plantar flexors in the lower extremities. A ground electrode will be applied over the patella. Standard skin preparation techniques (light abrasion and cleansing with alcohol) will be completed prior to application of the electrodes. EMG recordings will be amplified (Octopus AMT-8; Bortec Biomedical, Calgary, Alberta), band-pass filtered (10-1000 Hz), and sampled at 5000 Hz. Electromyographic (EMG) activity will be collected from all muscles bilaterally. TMS will be delivered with the stimulating coil positioned over the vertex at intensities ranging from 70 - 140% of "walking threshold". This threshold is a better estimate of excitability than conventional thresholding because during walking, EMG burst patterns and EMG amplitude differ between subjects, and walking threshold is typically lower than tonic contraction threshold, and much lower than rest threshold. Walking threshold is the stimulus intensity that results in MEPs just visible as time locked waveforms emerging out of background EMG. Pre-burst onset MEPs will also be recorded at an intensity that results in a MEP of ~ 500 μ V. This measure is important because we expect when the WAD is providing assistance, the

EMG burst amplitude may change, making it difficult to interpret changes in MEP amplitude assessed during the EMG burst. Subjects will be walking on a treadmill when magnetic stimulation is delivered. An optical motion switch will detect when a limb is in mid-swing and sends a pulse to software that in turn delays a TMS trigger pulse to coincide with a chosen cycle phase. Motor cortex excitability changes during walking will be examined by calculating the mean amplitude of 10 MEPs recorded from each muscle with and without WAD. A harness will be placed around the subject's pelvis and lower torso. The harness is attached to a rope and pulley system that is capable of supporting the subject's entire body weight in the upright position. A physical therapist (PT) will be in attendance at all times. Use of the harness and handrails, and the PT in attendance, will ensure that the subject is comfortable and secure at all times. Subjects will be provided with sufficient breaks between walking to avoid fatigue.

IV. Using the Walk Assist Device (WAD)

As part of the testing in this study, subjects will be asked to participate in body weight supported treadmill walking and/or over ground walking with the help of the WAD. All testing procedures will be with a licensed physical therapist or physical therapist assistant as described below.

Device Assisted Walking: The walk assist device (WAD) consists of a waist frame, rechargeable lithium ion batteries, hip actuators / motors, angle sensor and thigh frame. The WAD gently assists both forward and backward movements at a person's hip joints in a very smooth way with the electrical actuators. The electrical actuators are equipped with angular sensors to monitor walking speed, velocity, and the degrees of the forward and backward movement of the hip joints. Using the information from the sensors, the WAD gently assists the person towards normal walking patterns. However, most subjects are unaware of this manipulation because the assistive torque is

Study Number # NUSTU00022438

small. The WAD stops functioning when the subject stops walking and will in no way control walking or movement of the subject causing tripping or falling. The total weight of the WAS is approximately six pounds. All subjects will receive a thorough explanation of the structure and function of the WAD before the experiment to eliminate any concerns. Individual fitting of the WAD will be performed by the persons who developed the WAD to avoid any kind of discomfort to the subjects. The WAD also helps in conserving the subject's energy consumption during walking as the device utilizes the subject's inertia and gravity to assist walking. The WAD has been successfully used to assist walking in the elderly population and reduce energy consumption during walking in healthy controls.^{1, 2}

IV. Statistical Analysis

Paired comparisons of electromyographic, kinematic, kinetics, strength and metabolic data will be made within subjects between groups (un-assisted stepping, device-assisted stepping) using standard parametric (t-test, ANOVA) comparisons. Changes in clinical performance will be assessed using primarily ordinal measures, with statistical comparisons made using non-parametric tests. Correlation (Pearson or Spearman) will be made between clinical/functional assessments and kinematics/kinetics observed during device-assisted walking.

V. References

1. Effects of an automated stride assistance system on walking parameters and muscular glucose metabolism in elderly adults. Shimada H, Suzuki T, Kimura Y, Hirata T, Sugiura M, Endo Y, Yasuhara K, Shimada K, Kikuchi K, Oda K, Ishii K, Ishiwata K. Br J Sports Med. 2008 Nov;42(11):622-9. Epub 2008 Feb 28.

2. The use of positron emission tomography and [18F]fluorodeoxyglucose for functional imaging of muscular activity during exercise with a stride assistance system.Shimada H, Kimura Y, Suzuki T, Hirata T, Sugiura M, Endo Y, Yasuhara K, Shimada K, Kikuchi K, Hashimoto M, Ishikawa M, Oda K, Ishii K, Ishiwata K. IEEE Trans Neural Syst Rehabil Eng. 2007 Sep;15(3):442-8.

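### A subject whose physician refuses the sub-maximal graded treadmill test may still do the maximal-speed treadmill gait walk, for which no physician approval or heart-rate limit is stated

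*Combined protocol and SAP*

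**What the plan says.** Section III.B sets two exertion safeguards, each tied to a named activity.

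- For the metabolic measures: "Metabolic measures will always be measured at sub-maximal levels and will be stopped 75% of target heart rates".
- For the graded test, the physician's written agreement "will be obtained before allowing subjects to participate in sub-maximal graded treadmill test". If the physician declines, this excludes the subject's "participation only in the sub-maximal graded treadmill test; however they will be allowed to participate in the other tests involved in the study".

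The same section then describes the treadmill gait analysis, where "each will walk at pre-determined (0.5 km/hr increments) and maximal speed". Its outcome list includes "peak treadmill speed at minimal body weight support". For this walk it mentions a harness against falls, and at least three recordings of 30 seconds at various speeds.

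Protections that apply to everyone appear elsewhere. Inclusion e in Section II asks that subjects be "Medically stable with medical clearance to participate" and lists cardiopulmonary disease among the illnesses that must be absent. Exclusion b removes "Significant cardiorespiratory or metabolic disease that may limit exercise participation". Section IV on using the device adds: "All testing procedures will be with a licensed physical therapist or physical therapist assistant as described below".

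**The concern.** The sponsor judged that a treadmill test described as sub-maximal needs an individual written decision from the physician, on top of entry screening. A subject for whom that decision is negative has already passed screening, so the refusal tells the study something that screening did not. Yet the refusal is confined to the one test, and the subject goes on to a treadmill walk that includes maximal speed. The permission is explicit; this is more than an omission.

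A tester following the text would not need to ask the physician about the gait walk and would have no stated heart-rate limit during it. What is at stake is the safety of the few subjects, if any, who are refused. The documents give no refusal rate, and none is assumed here.

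**Working it through.** The plan gives no figure to reproduce on this point. The check sets each provision against each activity, then works out what the fix would cost in data.

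**Provisions by activity (Section III.B)**

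| Activity | Heart-rate stop stated | Physician's written approval stated | Open after refusal |
|---|---|---|---|
| Metabolic measures | Yes, 75% of target | Not separately | Unclear: depends on whether this is the graded test |
| Sub-maximal graded test | Not separately | Yes | No |
| Treadmill gait walk, increments and maximal speed | No | No | Yes, unless it is itself the graded test |

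**What the general protections cover.** Clearance and the two disease criteria act at entry. The harness is there to prevent falls. The therapist or assistant attends but is given no stopping rule for this walk. The 30 seconds is a recording period; total walking time is not capped. All reduce the risk, and none sets an exertion limit for the maximal-speed condition.

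**Two readings of the undefined graded test**

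1. It is separate from the gait walk. The sentences are then consistent: a refused subject skips one test and does the other. The gap is that nobody rules on the second.
2. It is the series of 0.5 km/h steps. The refusal clause can then be read as qualifying the general statement that each patient walks. Clarification would be enough, although a maximal-speed stage fits poorly in a test called sub-maximal.

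**Gait data kept by a subject limited to self-selected speed.** Levels kept = floor(speed in km/h ÷ 0.5), with km/h = m/s × 3.6. Assumptions: levels start at 0.5 km/h, and self-selected treadmill speed is 80% to 100% of over-ground speed.

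| Over-ground speed | At 100% | At 80% | Levels kept |
|---|---|---|---|
| 0.8 m/s (eligibility ceiling) | 2.88 km/h → 5 | 2.30 km/h → 4 | 4 to 5 |
| 0.4 m/s (stratum boundary) | 1.44 km/h → 2 | 1.15 km/h → 2 | 2 |
| 0.2 m/s (example; no lower speed limit is set) | 0.72 km/h → 1 | 0.58 km/h → 1 | 1 |

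If levels start at 1.0 km/h, each count falls by one, so the 0.2 m/s walker keeps none. Even with a 0.5 km/h start, a subject below 0.5 ÷ 3.6 = 0.14 m/s keeps none.

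**Sample size.** Section II recruits 15 and gives 12 as sufficient for the objective measures, without naming peak speed. If 12 is applied to peak speed, 15 − 12 = 3 subjects can lack maximal-speed data, provided nobody else is lost.

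**The case against.** The strongest reply is that harm is not shown. In the gait paragraph the word maximal describes speed; in the metabolic paragraph sub-maximal describes effort. Subjects choose 0.8 m/s or less over ground, so motor impairment may limit speed well before the heart does. Recordings are short. Everyone has been cleared to take part, with cardiopulmonary disease absent, and a harness and therapist are present. All of this stands, and it keeps the point modest.

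A reader might infer that the two sentences contradict each other however the graded test is understood. The documents do not support that: on the first reading above they are consistent, and on the second the specific clause can qualify the general one. A reader might also infer that refused subjects are sent to a harder test, or that they are unscreened. The first cannot be established, because the graded test is undefined and no cardiac load is given. The second is wrong, given inclusion e and exclusion b.

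What the reply does not remove is the explicit permission. The sponsor did not treat entry screening as enough for the sub-maximal test, and the text does not say why it should be enough for the maximal-speed walk after a physician has refused.

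**Conclusion.** The point holds as a modest participant-safety gap that is cheap to close. As written, a subject refused the graded test may walk on the treadmill at maximal speed with no physician decision about that walk and no stated heart-rate limit.

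Confidence is medium. The conclusion rests on reading the two safeguards as applying only to the activities they name. If the sponsor intends the graded test and the incremental gait walk to be one session, the approval may be meant to carry over, but the text does not say so. The number of subjects affected and the exertion involved cannot be determined from the documents.

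**What to change.** Amend the approval and non-approval sentences in Section III.B along these lines:

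> The physician's form covers, on separate lines, the sub-maximal graded treadmill test and treadmill gait walking above self-selected speed. A subject without approval on the second line is tested only at or below self-selected treadmill speed, with and without the device, and gives no peak treadmill speed.

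The protocol refers to self-selected speed only over ground, so the treadmill value must be set at the session, with one ceiling used for both conditions. The within-subject comparison then survives at the levels kept.

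The cost is one form line, a few protocol sentences and the maximal-speed data of subjects without approval. The slowest of them may keep only one 0.5 km/h level, or none.

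I would not extend the existing heart-rate stop to the peak-speed walks. Its base is undefined: if target is taken as 70%, 85% or 100% of maximum (assumed), 75% of target is 52.5%, 63.75% or 75% of maximum. A low limit could truncate a named outcome. Section IV also says the device saves energy, so the truncation could differ with and without it.

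### The marker-occlusion fallback can put two different instruments into one subject's paired hip or knee difference, and no rule prevents it

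*Combined protocol and SAP*

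**What the plan says.** Section III.B (Objective measure of motor and walking performance) lists among its outcomes "lower extremity kinematics during stepping, including peak hip, knee, and ankle joint kinematics during walking". The default measurement is optical: gait analysis "will be performed with use of a motion analysis system" and reflective markers. The same section has a fallback: where there is "visual occlusion of reflective markers during walking with assistance and/or devices, gait kinematics at the knee and hip will be detected by electrogoniometers", placed on both sides. The fallback does not name the ankle.

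Section IV (Using the Walk Assist Device) describes what is worn in the assisted condition: "The walk assist device (WAD) consists of a waist frame, rechargeable lithium ion batteries, hip actuators / motors, angle sensor and thigh frame".

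The Statistical Analysis section plans "Paired comparisons of electromyographic, kinematic, kinetics, strength and metabolic data will be made within subjects between groups (un-assisted stepping, device-assisted stepping"), by t-test or ANOVA. It has no term for instrument and no sensitivity analysis for it. No section asks for the same instrument in both conditions, for goniometers to be recorded during un-assisted walking, or for a check of agreement between the two systems.

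**The concern.** Pairing removes stable differences between subjects. It does not remove a difference that arrives together with the condition. If a subject's un-assisted hip angle comes from markers and the assisted hip angle from a goniometer, a constant offset between the two enters that subject's difference in full and reads as an effect of the WAD.

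The fallback is triggered by occlusion during walking with assistance or devices, and the WAD hardware sits at the waist, hip and thigh. Switching may therefore be more common in the assisted condition. The argument is stronger for the hip, the joint the WAD drives, than for the knee, where no WAD hardware is listed.

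Hip and knee angles are at stake. Ankle angles, ground reaction forces, EMG, metabolic cost, motor evoked potentials, GaitMat and clinical measures are not touched. The plan names no primary outcome, so it cannot be said that a primary analysis is affected.

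**Working it through.** **The plan's own figure.** Section II states that 12 subjects suffice and that 15 will be recruited. The 12 cannot be reproduced, because no alpha, power, effect size or SD is given. It is used here only as the analysed sample size.

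**Inputs from the documents.** n = 12 (Section II); paired comparison of un-assisted and device-assisted walking (Statistical Analysis); conditional switch to goniometers at hip and knee (Section III.B).

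**Assumptions.** Two-sided 5% paired t-test; no true device effect; paired differences normal with SD 1 apart from the offset; a common offset b between instruments of 0.4, 0.6 or 1.0 SD; various numbers switching.

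**Bias.** Let k₁ subjects switch only when device-assisted and k₂ only when un-assisted. Subjects who switch in both conditions or in neither contribute no offset. Then

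bias in the mean paired difference = ((k₁ − k₂)/12) × b.

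- k₁ = 9, k₂ = 3: (6/12) × b = 0.20 / 0.30 / 0.50 SD.
- k₁ = 6, k₂ = 3: (3/12) × b = 0.10 / 0.15 / 0.25 SD.

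**False-positive rate.** When all 12 switch only with the device, the test statistic is noncentral t on 11 degrees of freedom with noncentrality b√12. The other cases were simulated (400,000 runs).

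| Switch only when device-assisted | Switch only when un-assisted | b = 0.4 | b = 0.6 | b = 1.0 |
|---|---|---|---|---|
| 3 | 0 | 0.058 | 0.067 | 0.092 |
| 6 | 0 | 0.091 | 0.138 | 0.268 |
| 9 | 0 | 0.151 | 0.275 | 0.584 |
| 12 | 0 | 0.245 | 0.475 | 0.883 |
| 9 | 3 | 0.080 | 0.106 | 0.151 |
| 6 | 3 | 0.049 | 0.048 | 0.041 |

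In the last row the rejection rate stays near or below 5% because offsets of both signs also widen the spread of the differences. The mean is still biased, as shown above.

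**Other cases.**
- If the offset varies between subjects around zero (SD 0.6 or 1.0) and all switch, the rate is 0.050 and the bias is 0.
- If all 15 recruited subjects are analysed and all switch, the rate is 0.147, 0.438 and 0.949 for b = 0.25, 0.5 and 1.0.

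**Scale.** Under an assumed two-sided 5% test, 12 pairs have 80% power for a true difference of about 0.89 SD. A bias of 0.25 SD is 0.25/0.89, or about 28%, of that.

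**With one instrument per pair.** A constant offset cancels: the bias is 0, the rate returns to 5%, and the required sample size does not change.

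**The case against.** The harm needs three things that the documents do not show: enough occlusion to trigger the fallback despite eight cameras, more switching in one condition than in the other, and an offset with a non-zero mean. The high false-positive rates need 9 to 12 of 12 subjects switching in one direction with a large common offset. This stands, and it is why no size can be claimed.

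Occlusion is not peculiar to the WAD. Section II lets subjects walk "using assistive devices and bracing below the knee as needed", and Section III.B says "A harness attached to the suspension system will be used for all patients to prevent the patient from falling". Either could hide markers in both conditions. This also stands: the confounding may be only partial, and the case at the knee is thin.

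The fallback does not say whether a case of occlusion is a trial, a condition or a subject. If an affected subject were measured by goniometer throughout, no pair would be mixed. That reading is possible but not written, and the text equally permits switching by trial or by condition. The rule that would exclude mixed pairs is absent.

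One instrument per pair still leaves different subjects on different instruments. The planned correlations with device-assisted kinematics would then combine the two systems. That is true, but it is a separate point and does not undo the correction of the paired comparison.

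**Conclusion.** The concern holds. Followed as written, the plan can count an instrument offset as a WAD effect on hip or knee angles, and nothing in it prevents or detects this. The bias equals the net share of subjects switching in the assisted condition times the mean offset. Both quantities are unknown, so the consequence ranges from negligible (few switches, balanced switching or a zero-mean offset) to severe (most subjects switching one way with an offset near 1 SD). Every rate given rests on assumed offsets, switching counts and alpha. Confidence is moderate, because the gap in the text is clear and its practical size is not. It should be fixed: the remedy is cheap, and a mixed pair cannot be repaired later if goniometers were not recorded in the un-assisted trials.

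**What to change.** **Section III.B.** Record the electrogoniometers in every gait trial in both conditions, after confirming that they can be placed in the same position with and without the WAD.

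**Statistical Analysis.** State that, for each subject and joint, the paired difference is computed from one instrument: markers if usable in both conditions, otherwise goniometers in both. If neither is usable in both, set the pair to missing and report the count. Report how many subjects were analysed by each instrument and, where both were recorded in un-occluded trials, their agreement.

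**Cost.** Low. The goniometers are already in the protocol. The change needs extra set-up time for subjects already wearing markers and EMG electrodes, one placement check with the WAD fitted, and a few sentences of text. Subjects analysed by goniometer may be measured less precisely. If a hip goniometer cannot hold its position under the WAD frame, some hip pairs will be missing, which matters with 12 subjects.

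### Does leaving the 10-MEP mean untied to the pre-burst series let a change in EMG pass as a change in corticospinal excitability?

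*Combined protocol and SAP*

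**What the plan says.** Section III.C (Objective measure of corticospinal excitability during walking) describes transcranial magnetic stimulation (TMS) on the treadmill with and without the device. The relevant statements, in order:

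- Electrodes "will be applied over the muscle bellies of the quadriceps, hamstrings, ankle dorsiflexors and ankle plantar flexors in the lower extremities".
- "TMS will be delivered with the stimulating coil positioned over the vertex at intensities ranging from" 70 to 140% of walking threshold. That threshold is defined by MEPs becoming just visible above background EMG.
- A second series is added: "Pre-burst onset MEPs will also be recorded at an intensity that results in a MEP of" about 500 microvolts.
- The stated reason is that the device may alter muscle activity: "EMG burst amplitude may change, making it difficult to interpret changes in MEP amplitude assessed during the EMG burst".
- For timing, software "delays a TMS trigger pulse to coincide with a chosen cycle phase".
- The outcome is found by "calculating the mean amplitude of 10 MEPs recorded from each muscle with and without WAD".

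The Statistical Analysis section plans within-subject paired comparisons of electromyographic data, un-assisted against device-assisted, by t-test or ANOVA. It does not mention MEPs by name or any adjustment for background EMG. Section II (Subject Population) gives 12 subjects as sufficient and 15 to be recruited.

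**The concern.** MEP amplitude can depend on how active the muscle is when the pulse arrives. If the device changes burst EMG, an in-burst MEP can change with no change in the corticospinal pathway. The plan says as much and records pre-burst MEPs in response, but the outcome sentence never says that its 10 MEPs are the pre-burst ones. The word introducing the pre-burst series implies that another series exists, and the intensity and phase behind the mean are also left open. Read literally, the outcome could be computed from the data the plan itself calls hard to interpret, or an analyst could choose between series after seeing results.

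A second gap sits beside it. The plan does not say whether stimulator output is set once or reset in each condition. If the 500-microvolt level were reset with the device on, pre-burst amplitude would be equalised by design and a real change hidden.

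Excitability is one of three impacts named in the Overview, beside muscle activity and motor performance, so this is not a peripheral variable. The error could run either way: a spurious effect or a masked one.

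**Working it through.** **What the text commits to.** The plan has no figure on this point to reproduce, so the first check is a reading. The rationale for the pre-burst series and the outcome sentence stand in one paragraph, with two sentences on the treadmill and the trigger between them. The outcome sentence describes how amplitude is summarised (a mean of 10 per muscle and condition). It fits either series and assigns inference to neither. The Statistical Analysis section compares electromyographic data across the same two conditions, so a burst-EMG change would be looked at in the same study. Section III.C says that a MEP is read from the muscle's EMG, so that wording can reasonably include MEPs.

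**How large the error could be if in-burst MEPs alone were used.** Only n = 12 comes from the documents. Assumptions:

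- no true excitability change;
- MEP proportional to EMG to the power b, with b = 0.5 or 1;
- an EMG fall f of 5, 10 or 20%;
- SD of the within-subject log ratio 0.20, 0.30 or 0.50;
- paired t-test on log ratios, two-sided 0.05, df = 11, critical t = 2.201.

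Standardised shift: d = b × |ln(1 − f)| / SD. Noncentrality: d × √12. Example with b = 1, f = 20%, SD = 0.20: |ln 0.8| = 0.223, d = 0.223/0.20 = 1.116, noncentrality 1.116 × 3.464 = 3.87, rejection probability 93.9%.

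| EMG fall | b | SD 0.20 | SD 0.30 | SD 0.50 |
|---|---|---|---|---|
| none | any | 5.0% | 5.0% | 5.0% |
| 5% | 0.5 | 6.9% | 5.8% | 5.3% |
| 5% | 1 | 12.8% | 8.4% | 6.2% |
| 10% | 0.5 | 13.3% | 8.6% | 6.3% |
| 10% | 1 | 38.5% | 19.9% | 10.3% |
| 20% | 0.5 | 42.2% | 21.8% | 10.9% |
| 20% | 1 | 93.9% | 65.1% | 29.2% |

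The mechanism is real, but the answer is set almost wholly by assumed inputs. The device section points to a mild effect: "most subjects are unaware of this manipulation because the assistive torque is" small. The torque also acts at the hip, while the recorded muscles include those at the ankle.

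**Whether EMG adjustment of in-burst MEPs would be a clear gain.** Model: regress each subject's log MEP ratio on the log EMG ratio and test the intercept (df = 10), by simulation with 100,000 trials per setting and n = 12.

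- *EMG ratio measured without error.* With a 20% fall and b = 1, false positives are 5.1% adjusted against 88.2% unadjusted (EMG log-ratio SD 0.10, residual SD 0.20).
- *EMG ratio measured with error.* In the same setting, an error SD of 0.10 gives about 14% false positives after adjustment, and 0.20 gives 42%. In a milder setting (EMG log-ratio SD 0.20, residual SD 0.50) the figures are 5.5% and 8.1%.
- *Power.* For a true 30% rise in excitability with a 20% EMG fall, b = 0.5, EMG log-ratio SD 0.10 and residual SD 0.20, adjustment detects it in 36% of trials against 64% unadjusted. With b = 1, adjustment helps: 10 to 72% against 6 to 9%.

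Adjustment therefore wins in some settings and loses in others, and the documents do not show which applies.

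**The case for a change.** The strongest case for a change is that intent is not specification. Two series, a range of intensities and an unspecified phase allow several different 10-MEP means per muscle. Naming one in advance would cost little and would remove the choice. Naming the series would not be enough unless stimulator output were also stated to be the same in both conditions.

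The description is accurate: the sentence names no series, phase or intensity, and the output setting is unstated. What does not stand is the step from there to a flawed analysis. Investigators who wrote down the confounder and recorded a series to avoid it can be expected to rest the excitability comparison on that series. Resetting output to a fixed MEP size in each condition would leave the pre-burst comparison with nothing to measure, so constant output is the only reading under which that series serves its stated purpose.

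Confining the outcome to pre-burst MEPs also has a price. One vertex coil position and one output may not give a usable pre-burst response in every muscle, whereas the plan intends a mean for each. Some latitude over muscle and phase is reasonable in a small study that assesses a prototype device.

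**Conclusion.** The concern identifies missing detail, not a wrong rule. The plan recognises that in-burst amplitude is hard to interpret when EMG changes, collects the series that avoids the problem, and compares EMG itself between conditions. Bias arises only if in-burst MEPs are analysed alone, the pre-burst data are disregarded and any EMG change goes unnoticed; no passage directs this. Analysts can fill in the series, phase, muscles and constant output from the plan's own rationale.

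The size of any bias cannot be derived from the documents. Under the assumptions above, false declarations from in-burst data alone would lie between 5% and 94% at n = 12, and between 5% and 13% for an EMG fall of 5%. The one added method, EMG adjustment of in-burst MEPs, is an optional secondary analysis whose benefit depends on unknown scaling and measurement error. No change to the plan follows.

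This conclusion rests on the pre-burst series being collected as described and on output being held constant between conditions. If a report relied only on in-burst MEPs, or reset output with the device on, the concern would apply to that report.
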